8.2. Serum Concentrations

Blood samples for the determination of serum concentrations of AV-1 will be collected on Day 1 at the following time points: predose (within 15 minutes), and at 0.5, 1 (end of infusion), 1.25, 1.5, 2, 3, 4, 6, 8, 12, 24, and 48 hours after the start of the infusion and on Day 5 prior to discharge, and at the follow-up visits on Days 8 (+2), 15 (\pm 2), 22 (\pm 2), 29 (\pm 2),85 (\pm 5), and 120 (\pm 5) (or ET). AV-1 serum concentrations will be determined using a validated ECL ELISA method based on the MesoScale Discovery platform.

AV-1 serum concentration data will be summarized using descriptive statistics (N, n [non-missing values within the population], arithmetic mean, SD, CV%, median, minimum, and maximum) by dose group and scheduled sampling time. Individual and mean AV-1 serum concentration versus time data will be plotted by dose group. For ease of presentation, mean serum concentrations of AV-1 will be plotted by nominal time by dose group on both linear and semi-logarithmic scales.

Serum PK concentrations of AV-1 will be reported to the precision of the raw data in listing presentations; summary statistics for arithmetic mean, median, minimum, maximum, and SD will be reported to 3 significant figures; and CV% will be reported to 1 decimal place.

8.3. Serum Pharmacokinetic Parameters

The serum concentration-time data for AV-1 will be analyzed by non-compartmental analysis using Phoenix[®] WinNonlin[®] (Certara USA, Inc., Princeton, NJ) Version 8.0 or higher. Actual sampling times will be used for the estimation of all serum PK parameters.

PK parameters of AV-1 will be summarized using descriptive statistics by dose group. If data allow, the following PK parameters will be calculated:

Parameter	Description
C _{max}	Maximum observed serum drug concentration
T _{max}	Time to reach maximum observed serum concentration
AUC ₀₋₄₈	Area under the serum concentration-time curve from time 0 to 48 hours
	postdose, calculated using the linear trapezoidal method
AUC _{0-tlast}	Area under the curve from time 0 to the last quantifiable concentration,
	calculated using the linear trapezoidal method
AUC _{0-∞}	Area under the serum concentration-time curve from time 0 extrapolated
	to infinity, calculated as $[AUC_{0-tlast} + (C_t/\lambda_z)]$ where C_t is the last
	observed serum drug concentration. %AUCexp must be <0.20 to retain
	$AUC_{0-\infty}$ and associated parameters in the summary and statistical tables
t1/2	Apparent terminal half-life, calculated as: $\ln(2)/\lambda_z$
CL	Total serum clearance, calculated as Dose/AUC _{0-∞}
Vz	Volume of distribution during the terminal phase, calculated as
	$Dose/AUC_{0-\infty}$ * λ_z

In addition to the above PK parameters, which will be listed and summarized, the following parameters will also be listed to document the selection of data points used to estimate $t_{1/2}$ using non-compartmental procedures:

Parameter	Description
%AUC _{exp}	Percentage of the area extrapolated for calculation of $AUC_{0-\infty}$.
λ_z	Apparent terminal elimination rate constant, where λ_z is the magnitude of the slope of the linear regression of the log concentration versus time profile during the terminal phase.
Number of points	Number of data points used to estimate λ_z ; a minimum of 3 data points must be used, and C_{max} must not be included.
λ_z lower	Lower bound used for the estimation of λ_z .
λ_z upper	Upper bound used for the estimation of λ_z .
Rsq	r^2 , the coefficient of determination (goodness of fit statistic); visual inspection of the terminal slope will be performed. In general, λ_z may only be retained if $r^2 \ge 0.80$

Serum PK parameters for AV-1 will be presented in data listings and summarized using descriptive statistics (n, arithmetic mean, SD, CV%, median, minimum, and maximum) by dose group. Geometric means and geometric CV will be reported for AUC_{0-tlast}, AUC_{0- ∞}, and C_{max}. T_{max} will be summarized using the descriptive statistics median, minimum, and maximum only.

Serum PK parameters of AV-1 will be displayed to 3 significant figures in all data listings and summary tables, with exception of time variables (T_{max} , λz lower, and λz upper) which will be displayed to 2 decimal places.

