10.4.3 Pharmacokinetic Analyses

Serum concentration data will be listed and summarized by time point for each dose level using descriptive statistics (number of subjects, mean, SD, coefficient of variation [CV], minimum, median, and maximum). Serum concentration versus time profiles for each subject will be presented graphically. The mean serum concentrations versus scheduled time profiles will be presented graphically by dose.

The PK parameters of AV-1 will be analyzed based on the actual sampling times. All parameters will be calculated using the latest version of Phoenix[®] WinNonlin[®] (Certara USA Inc., Princeton, New Jersey) or SAS[®] (SAS Institute Inc., Cary, North Carolina). Pharmacokinetic parameters will be summarized by time point for each dose level using descriptive statistics (number of subjects, arithmetic mean, SD, CV, minimum, median, and maximum). Geometric means and geometric CV will be reported for AUC₀-tlast, AUC₀-∞, and C_{max}. The following serum PK parameters will be calculated as data permit:

C_{max}	Maximum observed serum concentration
T_{max}	Time to reach maximum observed serum concentration
AUC ₀₋₄₈	Area under the serum concentration-time curve from time 0 to 48 hours postdose, calculated using the linear trapezoidal rule method
AUC _{0-tlast}	Area under the serum concentration-time curve from time 0 to the last quantifiable concentration, calculated using the linear trapezoidal method
AUC₀-∞	Area under the serum concentration-time curve from time 0 extrapolated to infinity, calculated as [AUC _{0-tlast} + (C _t / λ_z)] where C _t is the last observed serum drug concentration. %AUC _{exp} must be <0.20 to retain AUC _{0-∞} in the summary and statistical tables
t _{1/2}	Apparent terminal half-life, calculated as $ln(2)/\lambda_z$
CL	Total serum clearance, calculated as Dose/AUC₀-∞
V_z	Volume of distribution during the terminal phase, calculated as Dose/AUC $_{0\infty}$ * λ_z

In addition to the above PK parameters, which will be listed and summarized, the following parameters will also be listed to document the selection of data points used to estimate t_{1/2} using noncompartmental procedures:

%AUC _{exp}	Percentage of the area extrapolated for calculation of $AUC_{0-\infty}$
λ_z	Apparent terminal elimination rate constant
Number of points	Number of data points used to estimate λ_z ; a minimum of 3 data points must be used, and C_{max} must not be included
λ_z lower (h)	Lower bound used for the estimation of λ_z

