- (l) Clinical laboratory testing will occur at Screening, Check-in, predose (within 60 minutes) and 48 hours after the start of the IP infusion on Day 1; and on Days 8, 15, 22, 43, 85, and 120. A complete list of assessments is provided in Section 7.2. Blood and urine samples will be collected under fasted conditions and prepared per the clinic's standard procedures.
- (m) Urine drug screen will occur at Screening and Check-in and on Days 22, 43, and 85 per the clinic's standard procedures and per Section 7.2.

- (n) Women of childbearing potential only. A serum pregnancy test will be performed at Screening and Check-in, and tests must be negative prior to enrollment and dosing, respectively.
- (o) After verification of eligibility, subjects will be randomly assigned before dosing on Day 1.
- (p) The start of the IP infusion will be called "0" hour and is denoted with grey shading. All doses of the IP will be administered intravenously over a period of 60 minutes. Subjects will maintain an upright (ie, seated or standing) position for at least 4 hours after the end of infusion.
- ^(q) Blood samples for PK analysis of AV-1 in serum will be collected predose (within 15 minutes); at 0.5, 1 (end of infusion), 1.25, 1.5, 2, 3, 4, 6, 8, 12, 24, and 48 hours after the start of infusion, Day 5 prior to discharge, and at the follow-up visits on Days 8, 15, 22, 29, 43, 57, 85, and 120 (or ET).
- A blood sample will be drawn on Day –1 and tested only if a suspected hypersensitivity reaction occurs during or following infusion on Day 1 at the discretion of the Investigator in consultation with the Sponsor. At the discretion of the Investigator, an additional blood sample will be drawn as soon as possible after the event occurs (Day 1) and again the following day (Day 2).
- (s) During fasting periods, subjects should have nothing to eat or drink except water from 10 hours prior to start of the IP infusion until 4 hours after the end of infusion.
- (t) During non-fasting periods when subjects are at the clinical site, subjects should receive standardized meals per the clinic's standard procedures that are scheduled at the same time in each treatment period during the study.

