- (1) Clinical laboratory testing will occur at Screening, Check-in, predose (within 60 minutes) and 48 hours after the start of the IP infusion on Day 1; and on Days 8, 15, 22, 43, 85, and 120. A complete list of assessments is provided in protocol Section 7.2 Blood and urine samples will be collected under fasted conditions and prepared per the clinic's standard procedures.
- ^(m) Urine drug screen will occur at Screening and Check-in and on Days 22, 43, and 85 per the clinic's standard procedures and per Section 7.2.
- ⁽ⁿ⁾ Women of childbearing potential only. A serum pregnancy test will be performed at Screening and Check-in, and tests must be negative prior to enrollment and dosing, respectively.
- ^(o) After verification of eligibility, subjects will be randomly assigned before dosing on Day 1.
- (p) The start of the IP infusion will be called "0" hour and is denoted with grey shading. All doses of the IP will be administered intravenously over a period of 60 minutes. Subjects will maintain an upright (ie, seated or standing) position for at least 4 hours after the end of infusion.
- ^(q) Blood samples for PK analysis of AV-1 in serum will be collected predose (within 15 minutes); at 0.5, 1 (end of infusion), 1.25, 1.5, 2, 3, 4, 6, 8, 12, 24, and 48 hours after the start of infusion, Day 5 prior to discharge, and at the follow-up visits on Days 8, 15, 22, 29, 85, and 120 (or ET).
- (r) A blood sample will be drawn on Day -1 and tested only if a suspected hypersensitivity reaction occurs during or following infusion on Day 1 at the discretion of the Investigator in consultation with the Sponsor. At the discretion of the Investigator, an additional blood sample will be drawn as soon as possible after the event occurs (Day 1) and again the following day (Day 2).
- ^(s) During fasting periods, subjects should have nothing to eat or drink except water from 10 hours prior to start of the IP infusion until 4 hours after the end of infusion. Water is permitted as desired except for the period of 1 hour prior to the start of the IP infusion until 1 hour after the end of the infusion.
- ^(t) During non-fasting periods when subjects are at the clinical site, subjects should receive standardized meals per the clinic's standard procedures that are scheduled at the same time in each treatment period during the study.

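### The linear trapezoidal rule overstates AV-1 AUC0-inf by about 1-4% with full sampling, and by more when late visits are missed; a linear-up/log-down rule removes most of this at almost no cost

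*SAP*

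**What the plan says.** Both documents fix the same integration rule. Protocol 10.4.3 defines AUC0-tlast "from time 0 to the last quantifiable concentration, calculated using the linear trapezoidal method", and SAP 8.3 repeats it for AUC0-48 and AUC0-tlast ("calculated using the linear trapezoidal method"). Neither gives a logarithmic rule for falling concentrations.

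The other parameters follow from that area. AUC0-inf adds C_t/lambda-z to AUC0-tlast. CL is "Total serum clearance, calculated as Dose/AUC"0-inf, and Vz also divides by AUC0-inf. SAP 8.3 takes lambda-z from a linear regression of log concentration on time, so it treats the terminal phase as exponential.

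Protocol Appendix A (17.1), footnote q, samples densely at first ("1.25, 1.5, 2, 3, 4, 6, 8, 12, 24, and 48 hours after the start of infusion, Day 5 prior to discharge") and then sparsely: "at the follow-up visits on Days 8, 15, 22, 29, 43, 57, 85, and 120 (or ET" visit). The infusion is short: "All doses of the IP will be administered intravenously over a period of 60 minutes".

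Three rules decide which subjects count:
- The PK population (SAP 4.2, protocol 10.4.1) needs the full dose and the samples through 1.5 hours only.
- Missing concentrations are left out of the calculations (SAP 8.1, protocol 10.5).
- The extrapolated share of AUC0-inf "must be <0.20 to retain" that parameter in the tables.

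**The concern.** After a one-hour infusion, serum concentration falls at every later sample. On a convex decline the chord between two samples lies above the curve, so each falling interval is overestimated. The error has one direction and does not shrink with more subjects. It grows with the length of the gap relative to the half-life, so it also grows when a late visit is missed.

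AUC and CL are secondary endpoints (protocol 3.3.2) of a first-in-human study meant to inform further development (protocol 2.2.1). What is at stake is the absolute level of reported exposure and clearance, and some avoidable spread between subjects who attended different late visits.

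**Working it through.** **No figure to reproduce.** The documents state no AUC, CL, half-life or bias for AV-1. The size has to come from an assumed profile.

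**Inputs from the documents.** 60-minute infusion; samples at 0, 0.5, 1, 1.25, 1.5, 2, 3, 4, 6, 8, 12, 24 and 48 h, then Days 5, 8, 15, 22, 29, 43, 57, 85 and 120 (protocol 7.2.2 and 17.1). Day d is placed d - 1 days after the start of infusion.

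**Assumed inputs.** Two compartments with V1 = 3 L, Q = 0.5 L/day, V2 = 2.8 L, and CL set to give terminal half-lives of 11, 16, 22, 29 and 36 days (CL = 0.462, 0.290, 0.202, 0.149 and 0.118 L/day). Lambda-z comes from the last three samples. Nominal times, no assay error.

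**Step 1: error in one interval.** For exponential decline at rate lambda over a gap g, linear area / true area = x coth(x), with x = lambda g/2. At a 22-day half-life, lambda = ln 2/22 = 0.0315 per day. For g = 28, x = 0.441 and the ratio is 1.064. For gaps of 7, 14 and 35 days it is 1.004, 1.016 and 1.099. Missing Day 85 leaves a 63-day gap (ratio 1.309). Missing Days 57 and 85 leaves 77 days (ratio 1.448).

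**Step 2: error in AUC0-inf.** True AUC0-inf = Dose/CL. Error = (trapezoid sum + C_t/lambda-z)/(Dose/CL) - 1.

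| Terminal half-life (days) | 11 | 16 | 22 | 29 | 36 |
|---|---|---|---|---|---|
| Linear, all samples | +3.6% | +2.8% | +2.2% | +1.6% | +1.2% |
| Linear, Day 85 missed | +5.3% | +5.8% | +5.3% | +4.2% | +3.3% |
| Linear, Days 57 and 85 missed | +10.6% | +12.2% | +10.8% | +8.3% | +6.3% |
| Linear-up/log-down, each of these cases | +1.0% | +0.7% | +0.5% | +0.4% | +0.3% |

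CL = Dose/AUC0-inf moves inversely: -3.5% to -1.2% with all samples, -5.5% to -3.2% without Day 85, and -10.9% to -5.9% without Days 57 and 85. For example, 1/1.122 - 1 = -10.9%.

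**Step 3: where the full-sampling error arises** (percentage points of AUC0-inf; sums differ from step 2 only by rounding).

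| Interval | 11 d | 16 d | 22 d | 29 d | 36 d |
|---|---|---|---|---|---|
| 0-48 h | 0.11 | 0.05 | 0.03 | 0.02 | 0.02 |
| 48 h to Day 29 | 2.21 | 1.29 | 0.81 | 0.56 | 0.42 |
| Day 29 to Day 57 | 0.69 | 0.54 | 0.35 | 0.22 | 0.14 |
| Day 57 to Day 120 | 0.58 | 0.95 | 1.00 | 0.85 | 0.67 |

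The last two gaps supply about one sixth of the error at 11 days (0.58/3.59) and about half at 36 days (0.67/1.24). AUC0-48 itself is off by only 0.25-0.46%.

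**Step 4: sensitivity to the profile.** A mono-exponential decline with half-life 10 to 35 days gives +2.6% to +0.9% with all samples. Bi-exponential profiles with a fast-phase half-life of 0.5-3 days and a terminal half-life of 14-28 days give +1.4% to +3.4%. The range of about 1-4% does not hang on one parameter set.

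**Step 5: do the inclusion rules catch the missed-visit cases?** Reading the 0.20 limit as a fraction, no. With Day 120 measured and Days 57 and 85 missing, the extrapolated share is 0.04% to 9.0% across these half-lives. The PK population rule stops at 1.5 hours.

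**Step 6: dose-proportionality slope (SAP 8.4).** r = 1000/30 = 33.3 and ln r = 3.507, so the window is 1 ± ln(1.25)/3.507 = 1 ± 0.064. A bias equal at all doses cancels in the slope. If the whole full-sampling range lined up with dose, from 1.24% at 30 mg to 3.59% at 1000 mg, the slope would move by ln(1.0359/1.0124)/3.507 = 0.0065, about a tenth of the margin.

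**The case against.** The strongest case against is that this is a method preference. The linear rule is stated consistently in both documents. With complete sampling it costs 1-4% on descriptive secondary endpoints, with six AV-1 subjects per dose, no hypothesis formally tested (protocol 10.1) and a sample size not based on power (SAP 4.1). Dose escalation under protocol 8.2.2 turns on safety review; protocol 3.1 also mentions PK data but names no parameter. The 6-12% figures need a subject who misses both Day 57 and Day 85 yet attends Day 120, and the documents give no missed-visit rate. An early withdrawal shortens the curve and does not by itself create that long gap.

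Most of this stands and limits the importance of the point. It does not remove it: the bias is known, one-directional and avoidable, and nothing in the plan filters out the subjects in whom it is large.

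Three stronger readings are tempting and are not supported:
- *The 28- and 35-day gaps cause the problem.* They supply at most 1.0 percentage point in this model when all samples are taken, because little of the AUC lies there.
- *The dose-proportionality conclusion is at risk.* With full sampling the slope shift is about 0.0065 against 0.064. A larger shift would need missed visits that track dose, and nothing in the documents suggests that.
- *The error will be 4-16%, because the SAP drops two samples.* SAP 8.2 omits Days 43 and 57, and SAP Appendix 1 footnote q lists PK samples "at the follow-up visits on Days 8, 15, 22, 29, 85, and 120 (or ET" visit). A 56-day gap would indeed give +4.2% to +13.4% in this model, and +4.3% to +15.5% for the mono-exponential case. But the SAP's own schedule table marks PK samples on both days, and the protocol collects them. This is a separate inconsistency to reconcile, not evidence that the samples will be left out.

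**Conclusion.** The point holds as a refinement of minor to moderate importance. The direction is certain for any convex decline. The size rests on an assumed half-life of 11-36 days and an assumed two-compartment profile. On that basis AUC0-inf is overstated by about 1-4% on the protocol schedule, by about 3-6% in a subject without Day 85, and by about 6-12% in a subject without Days 57 and 85. CL is understated correspondingly, and Vz by the same proportion as CL, since lambda-z does not depend on the integration rule. How many subjects fall in the last two groups is unknown. The claim that the extrapolation limit does not screen them out assumes that 0.20 means 20%. No decision rule in the plan is shown to change.

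**What to change.** In SAP 8.3 and protocol 10.4.3, replace the linear trapezoidal method by the linear-up/log-down trapezoidal method: linear while concentrations rise or stay equal, logarithmic while they fall. Apply it to AUC0-48 as well for uniformity, although that figure will hardly move. In every case above it reduces the AUC0-inf error to 1% or less.

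The rule can always be computed under the existing data handling. AUC0-tlast ends at the last quantifiable value, and a BLQ value between two quantifiable ones is already set to missing (SAP 8.1), so no logarithm of zero arises on the decline.

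The cost is one phrase in two sections and one software setting, with no new data or visits. It should be made before database lock. At the same time, the PK day lists in SAP 8.2 and SAP Appendix 1 footnote q should be reconciled with the SAP's schedule table and the protocol.

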The Investigator will inform the subject that already collected data will be retained and analyzed even if the subject withdraws from this study.

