5.2.2 Subject Replacement

Any subject who withdraws before completing the study but after receiving IP may be replaced at the discretion of the Investigator and in consultation with the Sponsor. Any replacement subject will be assigned to receive the same treatment as the subject he or she is replacing.

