10.2 Sample Size Considerations

This study will enroll a total of 40 subjects in 5 cohorts of 8 subjects each and up to 8 subjects for replacements as necessary. Each cohort will consist of 6 AV-1 treated and 2 placebo treated subjects.

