4.2. Analysis Populations

The Safety population will include all subjects who receive any amount of the IP. The safety population will also be used for anti-AV-1 antibody assessment.

The PK population will include subjects who receive the full dose of AV-1 and have at minimum all samples from predose through 1.5 hours from the start of infusion to have sufficient concentration data to support accurate estimation of at least 1 PK parameter.

5. Subject Disposition, Protocol Deviations, and Follow-up

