8.1. Data Handling

Serum concentrations that are below the limit of quantification (BLQ) will be treated as zero for calculation of descriptive statistics. Mean BLQ concentrations will be presented as BLQ, and the SD and CV will be reported as not applicable.

For PK analysis, BLQ values will be treated as zero with the exception that a BLQ value between 2 quantifiable concentrations will be set as missing. If consecutive BLQ concentrations are followed by quantifiable concentrations in the terminal phase, those concentrations after BLQ concentrations will be treated as missing.

Missing concentrations will be excluded from all calculations and PK analyses.

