8.4. Pharmacokinetic Statistical Analysis

Dose-proportionality for AV-1 will be evaluated for C_{max} , AUC_{0-tlast}, and AUC_{0- ∞}. A power model will be fitted to describe the relationship between Y (C_{max} , AUC_{0-tlast} and AUC_{0- ∞}) and X (dose) using the least-squares linear regression model [ln(Y) = ln(β_0) + β_1 ln(X)].

From each model, the intercept of regression line $[\ln(\beta_0)]$ and the slope of the regression line β_1 will be presented along with the 90% confidence interval (CI) of the slope. Dose-proportionality will be concluded if the 90% CI of the slope β_1 lies entirely within $[1+\ln(0.8)/\ln(r), 1+\ln(1.25)/\ln(r)]$, where r is a ratio that describes the dose range and is defined as the ratio of highest dose/lowest dose. If dose proportionality is not observed, then the lowest dose followed by the highest dose in succession will be removed, and the model will be fit again after the removal of a dose until dose proportionality is achieved or less than 3 dose groups remain.

The statistical analyses will be based on the PK population.

9. Anti-AV-1 Antibody Analysis

Blood samples for immunogenicity analysis will be collected at Check-in (Day -1) and on Days 29 (±2), 85 (±5), and 120 (±5) (or ET). A validated ECL ELISA method will be used for detection and confirmation of preexisting and treatment-emergent anti-AV-1 antibodies in serum samples based on the MesoScale Discovery platform that utilizes labeled AV-1 for detection of anti-AV-1 antibodies and treatment emergent antibodies.

Frequency and percentage of subjects who show detectable anti-AV-1 antibody signal in serum, including treatment-emergent anti-AV- antibodies, will be summarized for the safety population. Pharmacokinetic parameters may be displayed based on anti-AV-1 antibody status as applicable.

Anti-AV-1 antibody data will be presented in a data listing for the safety population.

10. Safety Analysis

All safety summaries and analyses will be conducted for the safety population.

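### A subject who leaves early contributes a cut-off AUC0-tlast to the geometric means and the dose-proportionality model, and no completeness rule stops it

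*SAP*

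**What the plan says.** - **Parameter.** SAP 8.3 defines AUC0-tlast as "Area under the curve from time 0 to the last quantifiable concentration". It sets no minimum for tlast.
- **Population.** SAP 4.2 admits subjects who received the full AV-1 dose and "have at minimum all samples from predose through 1.5 hours from the start of infusion". No later sample is required.
- **Use.** SAP 8.3 states "Geometric means and geometric CV will be reported for" AUC0-tlast, AUC0-inf and Cmax. SAP 8.4 fits the power model to the same three parameters and adds: "The statistical analyses will be based on the PK population".
- **Leavers.** Under Protocol 5.2.1, subjects are told that "already collected data will be retained and analyzed even if the subject withdraws from this study". The one stated exclusion from analysis is a subject who becomes pregnant after dosing. SAP 8.1 deals with samples never drawn: "Missing concentrations will be excluded from all calculations and PK analyses".
- **Replacement.** Protocol 5.2.2: "Any subject who withdraws before completing the study but after receiving IP may be replaced". This is discretionary, and nothing removes the replaced subject from the PK population. Protocol 10.2 allows "up to 8 subjects for replacements as necessary".
- **Guard on the sister parameter.** SAP 8.3 keeps AUC0-inf and its associated parameters in the tables only if %AUCexp is below 0.20, which I read as 20%. AUC0-tlast has no similar condition.

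**The concern.** When concentrations are followed to Day 120 or to the assay limit, AUC0-tlast approximates total exposure. When sampling stops because the subject left, it measures exposure over whatever time that subject happened to stay. Averaging the two lowers the dose group's geometric mean. In the regression on dose, the short value can tilt the slope and also widens its confidence interval.

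SAP 8.4 attaches a decision to that interval. If it does not lie within the limits, the lowest and then the highest dose group is removed and the model refitted. A dropout could therefore be reported as non-linear pharmacokinetics, or proportionality could be claimed over a narrower dose range. Early leaving is foreseen: Protocol 5.2.1 lists loss to follow-up, prohibited medication, blood donation and a positive urine drug screen among the reasons for stopping participation. Post-dose screens fall on Days 22, 43 and 85.

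**Working it through.** The plan states no power, precision or variability figure for this analysis, so there is none to reproduce. SAP 4.1 says the sample size does not come from a power calculation.

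**Inputs from the documents.** Doses of 30, 90, 250, 500 and 1000 mg with 6 active subjects each (30 in all); 90% CI of the slope; limits 1 + ln(0.8)/ln(r) to 1 + ln(1.25)/ln(r); visits as in Protocol 7.2.2. (The sampling list in SAP 8.2 omits Days 43 and 57.)

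**Assumptions.** Mono-exponential decline; half-life 21 days, varied from 14 to 28; CV 10% to 25%; true proportionality.

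**Limits.** r = 1000/30 = 33.3. The margin is ln(1.25)/ln(33.3) = 0.2231/3.5066 = 0.0636, so the slope interval must lie within 0.9364 to 1.0636. The sum of squares of ln(dose) is Sxx = 46.29, and t(0.95, 28 df) = 1.701. Even with a slope of exactly 1, the criterion needs a residual SD of ln(AUC) no larger than 0.0636 × √46.29 / 1.701 = 0.255, a CV of about 26%.

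**Share of the Day 120 area.** For last sample on day d and half-life h, f = (1 − 2^(−(d−1)/h)) / (1 − 2^(−119/h)). At Day 22 with h = 21, f = 0.500/0.980 = 0.51. One leaver among six multiplies the group geometric mean by f^(1/6).

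| Last sample | f (h = 21 d) | Geometric mean lower by |
|---|---|---|
| Day 8 | 21% | 23% |
| Day 22 | 51% | 11% |
| Day 43 | 77% | 4% |
| Day 85 | 96% | 1% |

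These geometric-mean effects do not depend on the CV.

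**Slope shift from one leaver.** Shift = ln(f) × (ln dose − mean ln dose)/Sxx. At 1000 mg, ln dose − mean = 1.599. Day 22 gives −0.673 × 1.599/46.29 = −0.023; Day 8 gives −1.559 × 1.599/46.29 = −0.054. Compare the margin of 0.0636.

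**Interval, worked example (CV 15%, h = 21, full-data slope set to 1).**

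- Complete data: 1.000 (0.963 to 1.037), passes.
- One 1000 mg leaver at Day 15: 0.966 (0.914 to 1.018), fails.
- At Day 22: 0.977 (0.933 to 1.020), fails.
- At Day 29: 0.983 (0.944 to 1.023), passes.
- That leaver's value left out: 0.995 (0.956 to 1.033), passes.

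**Simulated chance of concluding proportionality over all five doses** (h = 21, leaver at a random dose, leaving at a visit from Day 8 to Day 57):

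| CV | No leaver | One leaver |
|---|---|---|
| 10% | 99% | 62% |
| 15% | 77% | 41% |
| 20% | 37% | 20% |
| 25% | 10% | 4% |

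At CV 15% the one-leaver figure is about 52% for a 14-day and 36% for a 28-day half-life, and two leavers at 21 days give about 23%. With the truncated values left out, the figures are about 75% for one leaver and 70% for two. Repeat runs differ by up to about 3 points.

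**Timing.** With one leaver fixed at 1000 mg (CV 15%, h = 21), the chance is 33% for Day 22, 52% for Day 29, 69% for Day 43, 74% for Day 57 and 76% for Day 85.

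**Step-down.** With one 1000 mg leaver at Day 15 (CV 15%), 55% of simulated trials end with a claim for 90 to 500 mg only and 36% with no claim, against 9% with no claim on complete data.

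**The case against.** The definition of AUC0-tlast is conventional, and the text does fix the leaver's value: the area up to the last quantifiable sample, with undrawn samples ignored. A reader might infer that the plan is silent on scoring. It is not; what is missing is a condition on using the value. Protocol 10.4.3 permits additional analyses, but specifies none for this case.

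A reader might also take the replacement allowance, 8 of 48 or 17%, as the dropout the sponsor expects. The documents do not support that. It is a ceiling and includes placebo subjects, who contribute nothing to the PK model. Replacement itself helps only slightly: about 45% with one leaver and 27% with two at CV 15%.

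The pass rates rest on an assumed CV and half-life. From a CV of about 25% the criterion is seldom met even with complete data, so there is little to overturn. Leavers are asked to attend an early termination visit with a PK sample, which can extend tlast. If the leaving day is drawn only from the urine drug screen days (22, 43 and 85), the one-leaver pass rate at CV 15% is 63%. PK is a secondary objective, and the primary safety conclusions are untouched.

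All of this stands. It limits the size and likelihood of the effect. It does not explain why a half-complete area is modelled as AUC0-tlast when the same subject's AUC0-inf is judged too incomplete to report.

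**Conclusion.** The concern holds as a conditional gap confined to AUC0-tlast. Followed exactly, the plan pools truncated areas with 120-day areas. The mechanism is certain from the text; the probabilities are illustrations under stated assumptions.

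It would be too strong to say that any early leaver overturns the trial's proportionality conclusion. Cmax is unaffected. A leaver's AUC0-inf is usually dropped by the 20% rule: at a 21-day half-life the extrapolated share is 50% at Day 22 and 25% at Day 43. The practical result may be three models that disagree. One leaver after about Day 57 changes little. The effect is material mainly when an active subject leaves before about Day 43 and CV is about 20% or less. In that range, one leaver cuts the chance of a correct AUC0-tlast conclusion by roughly 17 points (CV 20%: 37% to 20%) to 37 points (CV 10%: 99% to 62%), averaged over leaving visits from Day 8 to 57. The rule should be set in advance, because choosing whom to exclude after seeing the data would itself be open to question.

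**What to change.** In SAP 8.3 and 8.4, state before unblinding:

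- AUC0-tlast is listed, but not summarized or modelled, when quantifiable sampling ended before a prespecified visit (for example Day 85) for any reason other than a BLQ result. This includes withdrawal, early termination and missed final visits.
- Those subjects' Cmax, AUC0-48 and any AUC0-inf that meets the retention rules stay in.
- The power model with all AUC0-tlast values is reported as a sensitivity analysis.

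Tying the rule to a visit keeps nearly complete profiles, such as one ending at Day 85 with about 96% of the area, and covers subjects who miss late visits without formally withdrawing. The cost is a short SAP addition and one extra model run. The number of subjects with AUC0-tlast falls by the number of early leavers; at CV 15% this takes the chance of concluding proportionality only from about 77% to 75% for one and 70% for two.
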